During hospital admission, EGD will be performed on all subjects and hemostasis therapy applied as necessary. The study team decided against mandating that EGD be performed within 24 hours of hospital admission. This is a pragmatic trial. The longer the duration between the inpatient EGD and the ED VCE the greater the likelihood of discrepancy in the findings that may be due to a change in the lesion as part of its natural course or due to treatments delivered. However, the primary objective of the study is not to evaluate diagnostic accuracy of the ED VCE. The study team decided it was more important to enroll subjects in a timely manner than exclude subjects because the inpatient EGD was not completed within 24 hours.

For the experimental CERA group, subjects will be monitored for a minimum of 4 hours after ingestion. VCE will be undergo a formal review after completion of the VCE by a staff gastroenterologist with extensive experience in VCEs of the small bowel, colon, and esophagus. Both research personnel and the gastroenterologist will undergo a capsule training program organized by Medtronic and receive accreditation after the training.

11. Subjects in the experimental arm who have no sign of active bleeding, show no serious endoscopic findings on capsule, and have stable hemoglobin, blood pressure and heart rate for at least 4 hours will be discharged from the ED. Discharged CE patients will be scheduled to have an outpatient EGD within 3 days post discharge. Patients will be instructed to return to the ED sooner if signs of new bleeding develops. The Research Coordinator will facilitate setting up this appointment for the patient.

Any subject in the experimental arm with a positive VCE or a negative VCE but has a drop in Hemoglobin  $\geq 3$  at 4 hours or an elevated HR or low BP will be admitted. A hemoglobin drop between 2 and 3 will NOT automatically transfer patient to active control arm. In these cases, decision to proceed will be up to discretion of treating physician. We anticipate that all admitted patients in the experimental arm will undergo EGD in the hospital (same as AC arm.)

12. Primary Outcome: (1) Percent Discharged Home. Assumption is that 100% of Active Control / standard risk assessment will be admitted.
13. Secondary Outcome: Sensitivity and specificity of VCE compared to EGD

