### 5.2 Subject Exclusion Criteria

1. Upper GI Bleed with hemodynamic instability (BP<90 mmHg, pulse>120 beats per minute, and Hgb < 9 g/dL)
2. High Risk Upper GI Bleed (Glasgow Blatchford Score\*  $\geq$  6)
3. Signs, symptoms or history of liver cirrhosis or liver failure
4. Signs, symptoms or history of decompensated heart failure or congestive heart failure
5. Presumed Pregnant, trying to conceive or breastfeeding
6. Known history of gastric cancer
7. Known history of gastric or esophageal varices
8. GI surgery within the last 6 months
9. Prior enrollment in the CHEER Study
10. Prisoner or Ward of State
11. Trouble swallowing, suspected bowel obstruction or perforation, per treating clinician
12. Past UGI tract surgery (e.g., Bilroth I or II, esophagectomy, gastrectomy, bariatric procedure) that changes Gastrointestinal anatomy
13. Known history of gastroparesis, esophageal stricture or Crohn’s disease
14. Altered mental status that limits the ability to swallow a capsule
15. Expected to have Magnetic Resonance Imaging (MRI) examination within 7 days
16. Consumed medications within the past 12 hours that may coat the upper GI tract such as antacids or sucralfate or Maalox and potentially limits capsule visualization
17. Patient either refuses or is unable to get traditional EGD
18. Patient does not have reliable contact information – no phone, no permanent address
19. Patient refuses
20. Unable to provide written consent
21. Non-English speaker
22. Suspected middle or lower GI bleeding
23. Treating ED Physician is not amenable to admission or discharge based on randomization or Video Capsule Endoscopy results.

\* As a modification, the GBS Score modified from the traditional GBS score to reduce the Hemoglobin cut-off for 6 points from 10g/dL to 9 g/dL (see Appendix B, CHEER 4; patient screening)

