**Blood Urea (mg/dL)**

<18.2 (0 points)

18.2-22.3 (2 points)

22.4-28 (3 points)

28-70 (4 points)

>70 (6 points)

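### Step 11 sets no haemoglobin level at 4 hours, so a CERA subject entering at 9.0 to just under 11.0 g/dL can fall below the trial's own entry limit and meet no numeric trigger

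*Combined protocol and SAP*

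**What the plan says.** Section 4.4, step 11, governs disposition in the CERA arm.

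- **Discharge.** Subjects with no active bleeding and no serious capsule finding who "have stable hemoglobin, blood pressure and heart rate for at least 4 hours will be discharged from the ED". No number is attached to 'stable', here or elsewhere.
- **Admission.** "Any subject in the experimental arm with a positive VCE or a negative VCE but has a drop in Hemoglobin" of 3 or more "at 4 hours or an elevated HR or low BP will be admitted".
- **Discretion.** "A hemoglobin drop between 2 and 3 will NOT automatically transfer patient to active control arm". Whether to go ahead is then left to the judgement of the treating physician.

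A haemoglobin level appears only at screening. Exclusion 2 in section 5.2 begins "High Risk Upper GI Bleed (Glasgow Blatchford Score" and sets the limit at 6 or more. The footnote there says the score was modified to "reduce the Hemoglobin cut-off for 6 points from 10g/dL to 9 g/dL". On the scoring form (18.6), a value below 9.0 g/dL earns 6 points in either sex, so it excludes on its own. Exclusion 1 also mentions 9 g/dL, but joins it by 'and' to blood pressure and pulse.

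Forms 18.7 and 18.8 record haemoglobin in g/dL, with date and time, before and after the capsule. Neither carries an action limit.

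**The concern.** A rule based only on the size of the fall protects least those who start lowest. A subject entering at 9.0 g/dL would have to reach 6.0 before the admission trigger applied. The modified score lets in patients from 9.0 to just under 10.0 g/dL, whom the 10 g/dL cut-off would have excluded, and they are the ones nearest the limit.

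The primary goal (section 3.1) is safe discharge of low-risk patients, and the primary outcome is Percent Discharged Home. A subject whose 4-hour haemoglobin would have kept her out of the trial hours earlier could be counted as a discharge. Because discretion is written to begin at a drop of 2, a site could easily read a smaller drop as stable. Another site could hold the same patient, and both would be following the protocol.

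**Working it through.** The plan states no figure to reproduce here; the check is threshold arithmetic.

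**Inputs.** Admission at a drop of 3 or more and discretion at 2 to 3 (step 11); GBS points and the eligibility limit of under 6 (form 18.6). Assumed: baseline is the pre-PillCam value and close to the screening value; the unit is g/dL; haemoglobin is read to 0.1 g/dL; a drop of exactly 2.0 counts as discretion.

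**Can such patients enter?** With haemoglobin 9.0-12.0, melena, and all other items zero:
- woman: 1 + 1 = 2, eligible; urea of 22.4 to under 28 adds 3, giving 5, still eligible;
- man: 3 + 1 = 4, eligible; urea of 18.2-22.3 adds 2, giving 6, excluded.

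**Where is the gap?** Let H be the entry value and V the 4-hour value, with V < 9.0. The drop is H − V. No numeric trigger is met when H − V < 2.0, so V must lie above H − 2.0 and below 9.0. That is possible only if H < 11.0.

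| Entry H (0.1 g/dL steps) | 4-hour values below 9.0 that meet no numeric trigger |
|---|---|
| 9.0 | 8.9 to 7.1 |
| 9.5 | 8.9 to 7.6 |
| 10.0 | 8.9 to 8.1 |
| 10.5 | 8.9 to 8.6 |
| 10.8 | 8.9 only |
| 10.9 to 11.8 | none: each is discretion or admission |
| 11.9 or more | none: each is admission |

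If a drop of exactly 2.0 is not in the discretion band, the gap extends to an entry of 10.9.

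**Example.** A woman enters at 9.5 with GBS 2, has a negative capsule and normal vital signs, and is 8.5 at 4 hours. The drop is 9.5 − 8.5 = 1.0, which meets no numeric trigger.

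**Weight of one patient.** 100 subjects at an assumed 1:1 allocation gives 50 in CERA; 1/50 = 2 percentage points of Percent Discharged Home.

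**How often would a 9.0 limit be crossed by chance?** Suppose true haemoglobin does not change and the difference between two draws has SD 0.2 to 0.5 g/dL (an assumption; the documents give no figure). The chance of a recorded value below 9.0 is Φ((8.95 − H)/SD).

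| H | SD 0.2 | SD 0.3 | SD 0.5 |
|---|---|---|---|
| 9.0 | 0.401 | 0.434 | 0.460 |
| 9.2 | 0.106 | 0.202 | 0.309 |
| 9.5 | 0.003 | 0.033 | 0.136 |
| 10.0 | 0.000 | 0.000 | 0.018 |

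Dilution by fluids would raise these figures.

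**The case against.** The strongest reply is that discharge is not the default. Missing an admission trigger sends nobody home: step 11 also requires stable haemoglobin, and a clinician may well judge 8.5 after 9.5, or 7.1 after 9.0, not to be stable. This stands. A reader might infer that the protocol requires such a patient to be discharged; it does not. It permits discharge if the fall is read as stable, and gives no number to settle that reading. The capsule, heart-rate and blood-pressure triggers also remain in force.

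Second, 9.0 g/dL is a step in an entry score, not a validated discharge threshold, and change-based rules are a legitimate choice for serial haemoglobin. Also true. The value is borrowed because it is the only haemoglobin level that by itself keeps a patient out of this trial.

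Third, a default that the physician can override does not make sites uniform. Correct: it moves the default and documents the exceptions, and some between-site variation will remain.

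Fourth, there are safeguards: outpatient EGD within 3 days, return instructions, contact at Day 7 and Day 30, and treatment of a major outcome after discharge as a potential major adverse event (section 2.3.1). They reduce the risk, but act after the patient has gone home.

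**Conclusion.** The gap is real and narrow. For entry at 9.0 to just under 11.0 g/dL (9.0 to 10.8 at 0.1 g/dL steps), a 4-hour value below 9.0 can meet no numeric trigger, and only the undefined word 'stable' stands against discharge. From 11.0 to just under 12.0 the discretion band or the admission rule covers it; from 12.0 the admission rule does.

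This is a cheap improvement for patient safety. A reader might infer a flaw in the statistical plan or bias in the primary comparison; the documents support neither, and the primary test is unaffected. How many patients fall in the gap is unknown, because no entry haemoglobin distribution is given.

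The conclusion rests on the pre-PillCam value being the baseline and g/dL the unit. Forms 18.7 and 18.8 make that the natural reading, but step 11 states neither. Form 18.8 is also not labelled as the 4-hour sample.

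**What to change.** Add to step 11:

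> A 4-hour haemoglobin below 9.0 g/dL is not stable, whatever the drop from the pre-PillCam value: admit by default unless the treating physician records why not.

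Next to Percent Discharged Home, report the number of discharged CERA subjects with a 4-hour haemoglobin below 9.0 g/dL.

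**Cost.** No new laboratory test or haemoglobin field is needed, since forms 18.7 and 18.8 already capture the values. The rule is a protocol amendment and needs IRB approval before use (section 15.2). The discharge rate may be slightly lower, mainly among those entering at 9.0 to about 9.5, where repeat-test variation or dilution can cross the limit; the recorded override is meant for them.

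**Timing.** The page with the Statement of Compliance is dated 9/27/19, while section 6.2 and Appendix A plan recruitment from April 2018 to April 2019. If enrolment has closed, only the reported count applies. If it is still open, the amendment changes a disposition rule behind the primary outcome partway through, so its effective date should be reported.

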## **10 ASSESSMENT OF SAFETY**

### **10.1 Unanticipated Problems**

#### ***10.1.1 Capsule Retention, Capsule Retention, Group Crossover***

### **10.2 Serious Adverse Events**

Serious adverse events will be reported immediately to the Study PI and the local IRB. Additional procedures are warranted for cases of serious adverse events which is defined by the FDA as a patient outcome that is:

- (1) Death;
- (2) Life-threatening, i.e., the patient was at substantial risk of dying at the time of the adverse event or it is suspected that the use or continued use of the product would result in the patient's death;
- (3) Hospitalization (initial or prolonged);
- (4) Disability, i.e., resulted in a significant, persistent, or permanent change, impairment, damage or disruption in the patient's body function/structure, physical activities or quality of life;
- (5) Congenital anomaly, i.e., there are suspicions that exposure to a medical product prior to conception or during pregnancy resulted in an adverse outcome in the child;
- (6) Requires intervention to prevent permanent impairment or damage.

If a patient in either group experiences any of the aforementioned six outcomes that may be possibly related to the research protocol, including but not limited to the following categories of risk:

- (1) Missed gastrointestinal lesion;
- (2) Capsule ingestion;
- (3) Capsule retention;
- (4) Delayed definitive care;

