### **11.2 Sample Size Considerations**

With 100 patients, we will have adequate power (i.e.  $\geq 80\%$ ) to detect a 25% difference or greater in admission rates for subjects with low risk lesions with p- value less than 0.05. We assume that the controls will a 100% admission rate. We anticipate 20% or less of all subjects to be diagnosed with a high-risk lesion, we are unlikely to have adequate power to detect a significant difference in the hospital admission rate between the two study groups.

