### **11.3 Final Analysis Plan**

The analysis will be conducted in several stages. First, we will compare the baseline characteristics of the two study groups to determine if randomization was successful. We will also compare the baseline characteristics of the study samples by enrollment site. Second, we will compare the VCE and EGD results and classify all study subjects according to whether there is a high versus low risk lesion present. The VCE and EGD results may differ because they are not being performed at the same time and GI bleeds can resolve or change so it is unlikely that there will be perfect agreement between the two modalities. In cases where one modality identifies a low risk lesion and the other one a high-risk lesion, we will classify the lesion as high risk. If the VCE could not adequately visualize the tract, we will classify the results according to the EGD. We will compare the sensitivity and specificity of VCE and EGD for identifying high risk lesions. Finally, we will separately compare the admission rates of high-risk lesions and low risk lesions between the two study groups. We will compare admission rates aggregated across the four study centers as well as within each study center.

For tertiary outcomes, we will compare the outcomes by study group using a chi-square test statistic if the outcome is categorical such as the presence of an adverse event and a t test (normally distributed) or median test (non-normally distributed) if the outcome is continuous such as hospital or ED length of stay.

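### Step 11 is inconsistent on which arm a capsule-arm subject belongs to after a haemoglobin drop, and the analysis plan never says how a transferred subject is counted

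*Combined protocol and SAP*

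**What the plan says.** Section 4.4, step 11, sets out disposition in the capsule (CERA) arm. A subject is admitted for a positive capsule study, or for a negative one accompanied by a haemoglobin fall of 3 or more at 4 hours, a raised heart rate or low blood pressure. Three sentences then follow in order:

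- The first states that "A hemoglobin drop between 2 and 3 will NOT automatically transfer patient to active control arm".
- The second leaves what happens after a fall of that size to the judgement of the clinician in charge.
- The third reads "We anticipate that all admitted patients in the experimental arm will undergo EGD in the hospital", and likens this to what happens in the control (AC) arm.

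Step 12 gives the endpoint: "Primary Outcome: (1) Percent Discharged Home". All controls are assumed to be admitted.

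Section 10.1.1, under unanticipated problems, is headed "Capsule Retention, Capsule Retention, Group Crossover". No text about crossover follows it.

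Section 11.3 opens with a baseline comparison of the two groups as a check on randomisation. It later says "we will separately compare the admission rates of high-risk lesions and low risk lesions between the two study groups", and for tertiary outcomes "we will compare the outcomes by study group using a chi-square test statistic" when the outcome is categorical, such as an adverse event. The document does not mention intention-to-treat, analysis as randomised, or an analysis population, and has no rule for counting a transferred subject.

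**The concern.** To say that a fall of 2 to 3 does not automatically transfer a subject makes sense only if some other fall does. The only other fall given is 3 or more. For 2 to 3, the treating physician decides, so a transfer after randomisation may also be discretionary. The destination named is a study arm.

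The subjects at issue are admitted, or are candidates for admission, and admission is failure on the primary outcome. If they were counted as controls, they would leave the CERA denominator because of their outcome. They would join an arm already assumed to be fully admitted, so the control rate would not move. CERA would look better with no change in care. Any adverse event in a subject who swallowed the capsule and then deteriorated would be counted in the control arm, in a trial whose stated aim is safe discharge.

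**Working it through.** **1. The plan's own figure.** Section 11.2 says "With 100 patients, we will have adequate power" (at least 80%) for a 25-point difference in admission among low-risk lesions, with controls at 100% and at most 20% of subjects high-risk. Allocation is not stated, so 1:1 is assumed. Low-risk subjects number 100 × 0.80 = 80, or 40 per arm.

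Power = Φ{[Δ − 1.96·√(2p̄(1−p̄)/n)] / √[(p₁(1−p₁)+p₂(1−p₂))/n]}, with p₁ = 1.00, p₂ = 0.75, p̄ = 0.875, Δ = 0.25, two-sided 5%.

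- n = 40: (0.25 − 1.96 × 0.0739)/0.0685 = 1.53, so power is 93.8%.
- n = 50: (0.25 − 1.96 × 0.0661)/0.0612 = 1.97, so power is 97.5%.

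The stated power holds. The issue is bias in the estimate.

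**2. Effect of moving subjects.** Let n be the CERA subjects randomised, D those discharged, and t the admitted subjects counted in AC instead.

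- As randomised: percent discharged = D/n.
- With t moved: percent discharged = D/(n − t).
- Shift = D·t/[n(n − t)], which is above zero for any t > 0 when D > 0.

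AC stays at 100% admitted because everyone moved is admitted. The difference between arms therefore shifts by the same amount.

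**3. Numbers.** The documents give no value for t. Three starting points are shown.

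*(a) Assumed 20 of 50 CERA subjects admitted, so D = 30:*

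| t | CERA admitted | CERA discharged | Shift (points) |
|---|---|---|---|
| 0 | 20/50 = 40.0% | 60.0% | – |
| 1 | 19/49 = 38.8% | 61.2% | 1.2 |
| 2 | 18/48 = 37.5% | 62.5% | 2.5 |
| 5 | 15/45 = 33.3% | 66.7% | 6.7 |
| 10 | 10/40 = 25.0% | 75.0% | 15.0 |

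*(b) The feasibility trial described in section 2.1: 37 randomised to capsule, 7 admitted, so D = 30:*

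| t | CERA discharged |
|---|---|
| 0 | 30/37 = 81.1% |
| 1 | 30/36 = 83.3% |
| 3 | 30/34 = 88.2% |
| 5 | 30/32 = 93.8% |

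*(c) Section 11.2's own effect size among low-risk lesions, the stratum section 11.3 compares: n = 40, D = 10:*

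| t | CERA discharged |
|---|---|
| 0 | 10/40 = 25.0% |
| 1 | 10/39 = 25.6% |
| 3 | 10/37 = 27.0% |
| 5 | 10/35 = 28.6% |
| 10 | 10/30 = 33.3% |

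**4. The sentences side by side.** The first sentence quoted from step 11 treats a haemoglobin fall as something that can change a subject's arm. The third treats an admitted CERA subject as still in the experimental arm and compares that arm with AC. Both cannot describe the same subject's study arm. Neither is an analysis rule, and section 11.3 supplies none.

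**The case against.** The case against is substantial.

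- **Section 11.3 points towards randomised groups.** Its first stage uses the two groups to judge whether randomisation worked, which makes sense only for groups as randomised. The same term then serves for the admission comparison. Step 5 of section 4.4 creates the arms by randomisation alone.
- **Transfer may mean a care pathway.** Step 5 describes AC as admission plus in-hospital EGD. Step 11 says that a fall of 3 or more leads to admission, and it keeps admitted subjects in the experimental arm.
- **The crossover heading is weak evidence.** It sits under unanticipated problems, which suggests something to report and not a planned reclassification.
- **The counts may be small.** In the feasibility trial the 7 admissions are attributed to active bleeding or endoscopic findings, not to haemoglobin falls. One transfer in example (a) moves the result by only 1.2 points.

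All of this stands as a limit on the claim. A reader might infer that the protocol plans to analyse transferred subjects as controls; it does not say so. A reader might also infer that every admission triggers transfer, which would drive CERA discharge to 100% whatever the capsule showed. The text links transfer only to a haemoglobin fall, and never to a positive capsule study, heart rate or blood pressure.

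The objection does not remove the contradiction within step 11 or supply a counting rule. An inference from the randomisation check is a thin safeguard when the protocol itself names a move to the other arm after randomisation.

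**Conclusion.** The point holds as an inconsistency with a conditional consequence. Step 11 gives two answers on the arm of a CERA subject after a haemoglobin fall (3 or more by implication, 2 to 3 possibly at discretion), and no section says how that subject is counted.

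If such subjects were counted as controls, CERA percent discharged would be biased upward. The shift is 1.2 to 15.0 points for 1 to 10 moved from 20 of 50 admitted, 2.2 to 12.7 points (83.3 − 81.1 and 93.8 − 81.1) for 1 to 5 moved from 30 of 37 discharged, and 0.6 to 8.3 points for 1 to 10 moved at the plan's own effect size. Adverse events would be misattributed in the same direction.

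The transfer counts, the 20 of 50 and the 1:1 allocation are assumptions. The direction does not depend on them, provided that everyone moved has been admitted and that some CERA subjects are discharged. The power statement is unaffected. The documents do not support saying that this bias is planned. It should still be closed off before analysis, because the choice would otherwise be left to the analyst and would act on the primary outcome.

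**What to change.** 1. **Section 4.4, step 11.** Reconcile the sentences so that transfer to active control refers to the care a subject receives and not to a change of study arm. Leave every haemoglobin threshold and disposition rule as it is; those are for the study team.
2. **Section 11.3.** Add: *Comparisons of admission and discharge, adverse events and length of stay analyse every subject in the arm to which they were randomised. A CERA subject who is admitted counts as not discharged in CERA. Crossovers are listed descriptively by arm, with reasons.*
3. **Section 10.1.1.** Add a line under the heading saying what counts as a group crossover and that it is recorded without changing the analysis arm.

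The cost model need not be included. Section 3.2 describes it as a three-strategy decision analysis for a base-case patient, not a comparison of the randomised arms.

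The cost is a few sentences in an amendment, with no added subjects or outcome data. Crossovers can be recorded on the existing deviation form.
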